13.4.1.6. ISI, HADS, EQ-5D-5L, and SF-36

The treatment group difference for change in ISI, HADS, EQ-5D-5L, and SF-36 total scores and published subscale scores from Baseline to peak value and to each scheduled evaluation will be summarized descriptively with 95% confidence intervals. The 95% confidence intervals for the treatment group differences will be calculated within the framework of ANCOVA. The ANCOVA will have treatment and total opioid dose (<90 MED, \geq 90 MED) as fixed factors and Baseline value as covariate. In addition, the treatment group difference will be tested within the ANCOVA framework.

Scoring the SF-36 is a 2-step process.

Step 1: Precoded numeric values are recoded per the scoring key given in Table 13. Note that all items are scored so that a high score defines a more favorable health state. In addition, each item is scored on a 0 to 100 range so that the lowest and highest possible scores are 0 and 100, respectively. Scores represent the percentage of total possible score achieved.

Step 2: Items in the same scale are averaged together to create the 8 scale scores. Table 14 lists the items averaged together to create each scale. Items that are left blank (missing data) are not taken into account when calculating the scale scores. Hence, scale scores represent the average for all items in the scale that the respondent answered.

Item Number	Original Response Category	Recoded Value
1, 2, 20, 22, 34, 36	1	100
	2	75
	3	50
	4	25
	5	0
3, 4, 5, 6, 7, 8, 9, 10, 11, 12	1	0
	2	50
	3	100
13, 14, 15, 16, 17, 18, 19	1	0
	2	100
21, 23, 26, 27, 30	1	100
	2	80
	3	60
	4	40
	5	20
	6	0
32, 33, 35	1	0
	2	25
	3	50
	4	75
	5	100

 Table 13:
 Recoding Items for the Short Form Health Survey

Table 14: Definition of Average Scale Scores for Short Form Health Survey

Scale	Items Averaged for Scale Score	
Physical functioning	3 4 5 6 7 8 9 10 11 12	
Role limitations due to physical health	13 14 15 16	
Role limitations due to emotional problems	17 18 19	
Energy/fatigue	23 27 29 31	
Emotional well-being	24 25 26 28 30	
Social functioning	20 32	
Pain	21 22	
General health	1 33 34 35 36	

13.4.1.7. Daily Dose of Opioids and Number of Non-Opioid Concomitant Medications for Withdrawal Symptoms

The following endpoints will be summarized descriptively for each study day:

- Change from Baseline to final, daily opioid dose, expressed as MED and as a percentage of this baseline MED
- Number of non-opioid concomitant medications for withdrawal symptoms used by study day

13.4.2. Safety Analysis

All safety analyses will be performed on the Safety Population using the treatment actually received. All safety summaries will be descriptive; no statistical testing will be performed.

13.4.2.1.1. Adverse Events

A TEAE is defined as an AE with an onset that occurs after receiving study drug, or a continuing AE diagnosed prior to the date of first dose of study drug, which increases in severity after the start of dosing. AEs will be categorized by system organ class and preferred term with the Medical Dictionary for Regulatory Activities.

Summary tables for TEAEs will include number and percent of subjects experiencing TEAEs by system organ class and preferred term. If a subject has more than 1 TEAE that codes to the same preferred term, the subject will be counted only once for that preferred term. Similarly, if a subject has more than 1 TEAE within a system organ class category, the subject will be counted only once in that system organ class category.

The following TEAE summaries will be provided:

- Overall summary of TEAEs
- TEAEs by system organ class and preferred term
- Drug-related TEAEs by system organ class and preferred term
- TEAEs by system organ class, preferred term, and severity

Serious TEAEs and TEAEs leading to study drug discontinuation will be identified.

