Enhanced treatment options for emerging opioid withdrawal symptoms during opioid taper regimens may permit development of more efficient tapering protocols, which in turn would have significant

impact on reducing risk to patients on chronic opioids and may positively impact health economic outcomes.

There is a notable lack of well-controlled data on the opioid withdrawal syndrome during an opioid taper in chronic non-cancer pain patients. Gradually tapering a patient's opioid dose with small reductions in dose over a prolonged period of time is a practice inherently designed to mitigate the potential for opioid withdrawal. LUCEMYRA's effectiveness in treating opioid withdrawal symptoms has been established in the setting of abrupt opioid discontinuation; however, has not been thoroughly evaluated in the setting of an opioid taper. Opioid tapers are often conducted over several weeks, if not months, resulting in the potential for at least cumulative use of LUCEMYRA for beyond 14 days. A clinical trial is necessary to assess for a signal of serious hypotension, bradycardia, syncope, hepatotoxicity, or rebound hypertension, or identify potential unexpected serious risks of long-term use of LUCEMYRA in the setting of an opioid taper as the majority of the existing safety data for LUCEMYRA is on less than 14 days of use. This pilot study is intended to inform critical study design elements for a future pivotal study to assess the safety and efficacy of LUCEMYRA for use beyond 14 days in the setting of an opioid taper.

Methodology:

This is a pilot, multicenter, randomized, double-blind, placebo-controlled, outpatient clinical trial to assess the safety and tolerability, and to estimate the effectiveness of LUCEMYRA for mitigating the symptoms of opioid withdrawal in the setting of an opioid taper in subjects with chronic non-cancer pain.

After a Screening period of up to 28 days, subjects will begin a planned 14-day complete taper of their pre-study opioid and will be randomly assigned (1:1) to either LUCEMYRA or matching placebo. Study drug will be administered through the opioid taper and for 5 days after the opioid taper is completed. Study drug will then be tapered over a 4-day period for a total of approximately 21 days exposure to study drug (Figure 1).

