- ¹ Phone call will take place on Day 25, to check on the subject's well-being and to assess how the subject is feeling.
- ^m Phone calls will take place on Days 32, 39, and 46, to check on the subject's well-being and to assess how the subject is feeling.
- ⁿ Reminders contacts may be done via phone, text, or other electronic message. Remind the subjects about opioid dose reductions or, at Day 17, study drug dose reductions.
- Opioid dose will be decreased 50% from baseline MED beginning with the last dose of the day on Day -1, an additional 25% of baseline MED beginning on Day 6, and a final 25% (to dose of zero) beginning on Day 13. Opioid dose reduction may not occur on a Friday or Saturday unless the clinic can accommodate

subjects on Saturday and Sunday. Subjects who experience intolerable withdrawal symptoms despite increasing their dose of study drug to the maximum tolerated dose will be allowed to pause the opioid taper once. See Table 3 for the opioid taper schedule for subjects who must pause the taper.

- ^p Detailed study drug dosing information can be found in Section 9.2.3. Study drug taper begins on Day 18.
- ^q Subject interview will be conducted via a centralized interviewer through a phone call. The interview should take place no more than 5 days after the EOS Visit.
- ^r Training includes when to call the site due to symptoms of hypertension or hypotension, or if the subject records a vital signs measurement that meets the criteria to contact the site.
- ^s Training includes recording all pharmacologic and non-pharmacologic concomitant treatments (including opioid medications), study drug dose administration, scale assessments for both pain (Average Daily and Worst Daily NRS) and opioid withdrawal scales (SOWS-Gossop, SOWS-Handelsman, and MCGI-Subject), and recording of at-home vital signs (during study drug taper and through EOS only).

	Screeni	ing ^a							Study 1	Drug	Admi	nistra	tion ^b									Safety I	Follow-ı	ap
Method	Screenin g	RC	Visit 1	PC 1	Visit 2	RC		PC 2	Visit 3	RC		PC 3	Visit 4	RC		PC 3P	Visit 4P	RC	PC 4	Visit 5	PC 5	EOS	PCs 6,7,8	30-day PC 9
Timing	Days -28 to -2	Day -1	Day 1	Day 2	Day 3	Day 5	Day 6	Day 7	Day 8	Day 12	Day 13	Day 14	Day 15	Day 18	Day 19	Day 20	Day 21	Day 23	Days 24- 27	Day 28	Days 29- 33	Day 34		Follow -up ^c
Visit window					±1 day				±1 day				±1 day				±1 day			±1 day		±1 day		
Informed consent and HIPAA authorization	Х																							
Inclusion/exclusio n	Х																							

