6. TRIAL OBJECTIVES AND PURPOSE

6.1. **Primary Objective**

The primary objective is to evaluate the safety and tolerability of LUCEMYRA versus placebo when used during an opioid taper in subjects with chronic non-cancer pain.

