7.4. Duration of Subject Participation

The study duration for each subject will be up to 85 days. The Screening period is up to 28 days, the study drug administration period (including a 4-day study drug taper) is 21 to 27 days (the latter for those requiring an extended opioid taper), and a 30-day safety follow-up period.

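### The TEAE tables pool every onset from first dose to 30 days after last dose, so they cannot show which events began after Day 14 or after study drug was stopped

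*Combined protocol and SAP*

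**What the plan says.** The Rationale in Section 3.1 gives the reason for the trial: "A clinical trial is necessary to assess for a signal of serious hypotension, bradycardia, syncope, hepatotoxicity, or rebound hypertension". It adds that "the majority of the existing safety data for LUCEMYRA is on less than 14 days of use", and says that the pilot should inform the design of a later pivotal study of use beyond 14 days. The formal objective in Section 6.1 names no period: "The primary objective is to evaluate the safety and tolerability of LUCEMYRA versus placebo when used during an opioid taper".

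On exposure, Section 7.4 says that "the study drug administration period (including a 4-day study drug taper) is 21 to 27 days". A footnote to Table 2 says "Study drug taper begins on Day 18"; on the pause schedule, Table 3 puts this at Day 24. Section 12.2.3 collects AEs from the start of dosing on Day 1 until 30 days after the last dose.

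Section 13.4.2.1.1 defines a TEAE without any sub-period and plans: "Summary tables for TEAEs will include number and percent of subjects experiencing TEAEs by system organ class and preferred term". It lists four summaries: overall, by system organ class and preferred term, drug-related, and by severity. On counting it says: "If a subject has more than 1 TEAE that codes to the same preferred term, the subject will be counted only once" for that term. The same rule applies within a system organ class. Serious TEAEs and those leading to study drug discontinuation are to be identified. Section 13.4.2.1.3 sends clinically significant ECG deteriorations into the TEAE summaries. Section 12.1.2 makes symptomatic hypotension, and every confirmed hypertensive reading, an AE.

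Vital signs and laboratory values are summarised as change from baseline, by scheduled evaluation (Sections 7.2.1 and 13.4.2.1.4). Safety summaries are descriptive, without tests (Section 13.4.2). Section 13.1 calls the chapter an overview and leaves further analyses to a statistical analysis plan, of which no separate text is included.

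**The concern.** The reason given for running the trial is tied to time: what happens after two weeks on drug, and what happens on coming off it. The TEAE summaries have no time dimension. One percentage per preferred term mixes dose initiation, which existing data already cover, with continued use after Day 14, the 4-day study drug taper and 30 days off drug.

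The counting rule compounds this. A subject with dizziness on Day 2 and again on Day 18 contributes one count, and the table does not say when. Subjects who left before Day 15 stay in the denominator although they were never exposed in the late window.

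At stake is what the pilot can pass on to the pivotal study. An event confined to the first days and an event that emerges late or on stopping have different implications for that design, and the planned tables would show them alike.

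**Working it through.** **1. The plan's own precision figure.** Section 13.2 gives a 95% half-width of 0.24 at 20 per group and 0.17 at 40 per group, for a difference of 0.2 in the incidence of adverse withdrawal events. The two rates are not stated. Taking 0.10 and 0.30 (0.70 and 0.90 give the same), the half-width is 1.96 × √[(0.10×0.90 + 0.30×0.70)/n] = 1.96 × √(0.30/n).

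- n = 20: 1.96 × √0.015 = 0.240
- n = 40: 1.96 × √0.0075 = 0.170

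The figure reproduces without a continuity correction. It is used in step 5 only as a yardstick.

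**2. How the AE collection window divides.** Inputs are Section 7.4, Section 12.2.3 and the footnotes to Tables 2 and 3. The total is the last dosing day plus 30.

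| Onset period | Standard | With taper pause |
|---|---|---|
| Days 1-14 | 14 days (27%) | 14 days (25%) |
| Day 15 to start of study drug taper | Days 15-17: 3 (6%) | Days 15-23: 9 (16%) |
| Study drug taper | Days 18-21: 4 (8%) | Days 24-27: 4 (7%) |
| After last dose | 30 days (59%) | 30 days (53%) |
| Total | 51 days | 57 days |

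On-drug time after Day 14 is 3 + 4 = 7 of 51 days (14%), or 9 + 4 = 13 of 57 (23%).

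**3. What a pooled percentage can hide.** Let e be the risk of a given preferred term in Days 1-14, and l the later risk among subjects without an early event. The pooled incidence is P = 1 − (1 − e)(1 − l), so l = 1 − (1 − P)/(1 − e). For an illustrative P = 44%:

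- e = 40%: l = 1 − 0.56/0.60 = 6.7%
- e = 30%: l = 1 − 0.56/0.70 = 20%
- e = 20%: l = 1 − 0.56/0.80 = 30%
- e = 10%: l = 1 − 0.56/0.90 = 37.8%

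These four time courses give the same table entry.

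**4. Late events that add nothing to the count.** If early and late events of a term are independent, the share of late-event subjects already counted is e × l / l = e. At e = 30%, 30% of subjects with a late event leave the pooled count unchanged. Independence is an assumption. If the same subjects tend to be affected twice, the share is larger.

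**5. What a by-period table could deliver.** The documents give no retention figure, so 15 to 30 per arm at risk is an assumed range. The half-width uses the step 1 formula. The chance of at least one case in an arm is 1 − (1 − p)^n.

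| At risk per arm | Half-width, 0.10 v 0.30 | Chance of ≥1 case, p = 5% | p = 10% |
|---|---|---|---|
| 30 | 0.196 | 0.785 | 0.958 |
| 24 | 0.219 | 0.708 | 0.920 |
| 20 | 0.240 | 0.642 | 0.878 |
| 15 | 0.277 | 0.537 | 0.794 |

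**6. Whether other summaries fill the gap.** On the standard schedule, clinic vital signs fall on Days 15, 22 and 28: on drug after Day 14, just after the last dose, and a week later. Home readings are taken twice daily from Day 18 until the end-of-study visit. Chemistry falls on Day 15 and at end of study. Blood pressure, pulse and liver tests are therefore resolved in time, as changes from baseline. Syncope has no planned summary outside the TEAE tables. ECG deteriorations, symptomatic hypotension and confirmed hypertension are counted as events only there.

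**The case against.** The strongest reply is that timing is visible elsewhere. Of the five signals named in the Rationale, all but syncope have measurements at dated visits, and home readings cover the drug taper and the first week off drug. This stands, and it limits the point. A reader might infer that neither period can be seen anywhere in the planned output; the documents do not support that. But a mean change by visit does not give the incidence of an event, and it can stay flat while a few subjects have serious falls or rises.

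Second, the primary objective is general safety, and the Rationale speaks of serious events, which Section 13.4.2.1.1 says will be identified. This is fair as to the objective. Identifying serious cases still does not give incidence by period and arm.

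Third, Section 13.1 calls the chapter an overview. A reader might infer that no by-period analysis will ever be done; the text shows only that Section 13 omits one. However, where that chapter leaves something specific to the analysis plan it says so, as for criteria on laboratory values and vital signs. The AE section leaves nothing on timing.

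Two further over-readings should be avoided. The counting rule is once per preferred term and once per system organ class, not once per subject for all events. And the 14% and 23% are shares of calendar time, dominated by the 30-day follow-up; they do not measure bias or lost events.

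Finally, a by-period table has limits of its own. Denominators after Day 14 are subjects who remained on drug, so the comparison is no longer fully randomised if drop-out differs by arm. Counting by onset misses an early event that persists. On the standard schedule the opioid is planned to reach zero from Day 13 (Day 19 with a pause), so withdrawal overlaps the late window. These limits affect how the table is read. They do not argue against producing it.

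**Conclusion.** The point holds for the TEAE tables. As written, they cannot attribute syncope, symptomatic hypotension or clinically significant ECG deteriorations to use after Day 14 or to the time after stopping, although the Rationale gives safety beyond 14 days and rebound hypertension as reasons for the trial. By-visit vital signs and chemistry recover part of the information.

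The window shares follow from the schedule alone. The illustration that one pooled percentage fits opposite time courses rests on assumed rates, and the masking share also rests on independence. How many events would be misplaced in practice cannot be derived from the documents. This is a worthwhile, inexpensive addition to a descriptive pilot. It does not make the pooled tables wrong, and the sample size is unaffected.

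**What to change.** In Section 13.4.2.1.1, keep the pooled tables and add TEAE incidence by treatment arm and onset period:

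- Days 1-14
- Day 15 to the start of the study drug taper
- study drug taper
- after last dose

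Restart the once-per-term and once-per-class counts in each period. Use as denominator the subjects at risk at the start of that period. Define the periods by each subject's actual dosing dates, so that subjects who pause, and those who discontinue early and taper study drug before Day 15, are classified correctly. If the separate analysis plan already contains such a table, a cross-reference is enough.

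State with the table that periods after Day 14 on drug include only subjects still taking study drug, that the results are descriptive and to be read against placebo, and that an event persisting from an earlier period is not recounted.

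The cost is a little more table programming. AE contacts already fall around the cuts (Days 14, 15, 19, 22, 25 and 28 on the standard schedule), so no extra subjects, visits or tests are needed. The price in interpretation is small denominators: at an assumed 20 per arm, an event with a true risk of 5% has a 64% chance of appearing at all in that arm.

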- ¹ Phone call will take place on Day 31, to check on the subject's well-being and to assess how the subject is feeling.
- ^m Phone calls will take place on Days 38, 45, and 52, to check on the subject's well-being and to assess how the subject is feeling.
- ⁿ Reminders contacts may be done via phone, text, or other electronic message. Remind the subjects about opioid dose reductions or, at Day 24, study drug dose reductions.
- ^o Opioid dose will be decreased 50% from baseline MED beginning with the last dose of the day on Day -1. The opioid dose will be decreased or maintained beginning on Day 6. The opioid dose will be decreased an additional 25% of baseline MED or maintained beginning on Day 13. A final 25% (to dose of zero) reduction will be made beginning on Day 19. Subjects who experience intolerable withdrawal symptoms despite increasing their dose of study drug to the maximum tolerated dose will be allowed to pause the opioid taper once. Pausing the opioid taper includes either a return to the last stable opioid dose for the remainder of the current opioid dose reduction period (eg, if a subject experiences intolerable withdrawal at the second reduction stage [25% of baseline MED], they can return to the first reduction dose [50% of baseline MED]), or remaining on the current opioid dose instead of reducing at the next scheduled reduction, resulting in an overall extended opioid taper period and study duration. In this scenario, a subject will taper to a dose of zero beginning on Day 19. Opioid dose reduction may not occur on a Friday or Saturday unless the clinic can accommodate subjects on Saturday and Sunday.
- ^p Detailed study drug dosing information can be found in Section 9.2.3. Study drug taper begins on Day 24.
- ^q Subject interview will be conducted via a centralized interviewer through a phone call. The interview should take place no more than 5 days after the EOS Visit.
- ^r Training includes when to call the site due to symptoms of hypertension or hypotension, or if the subject records a vital signs measurement that meets the criteria to contact the site.

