12.1.2. Vital Signs

Orthostatic vital signs will be measured in-clinic. Orthostatic vital signs will be measured first after the subject has been sitting for at least 5 minutes (systolic/diastolic blood pressure, pulse, and temperature) and then after the subject has been standing for at least 3 minutes (systolic/diastolic blood pressure and pulse). On Day 1, orthostatic vital signs should be assessed pre-dose and 1-hour post-dose of study drug. A post-dose assessment is not required after Day 1. When repeat vital signs are performed, temperature does not need to be collected (only systolic/diastolic blood pressure and pulse).

Resting vital signs (systolic/diastolic blood pressure and pulse) only will be measured at home using a vital sign monitor during phone calls after dose reductions, and every day during the 4-day study drug taper through the EOS Visit. Resting vital signs will be measured after the subject has been sitting quietly for at least 5 minutes and, during the study drug taper and after, will be taken twice daily, once in the morning and once in the evening.

Subjects should contact the Investigator if they experience signs or symptoms of hypotension, bradycardia, or orthostasis (eg, lightheadedness, slow heart rate, dizziness, feeling faint at rest or when standing up) or hypertension (eg, pounding headache, dizziness, palpitations). Subjects should contact the Investigator if they record an at-home vital signs measurement reaching or exceeding a systolic blood pressure of ≥ 180 mmHg, diastolic blood pressure ≥ 105 mmHg, or heart rate of ≥ 120 bpm. Symptomatic episodes of hypotension should be captured as an AE. Confirmed instances of meeting criteria for hypertension should be captured as AEs regardless of symptomology.

During phone calls, the Investigator should ask the subject for a vital sign measurement and review subject-measured at-home vital signs.

Blood pressure and pulse measurements taken in-clinic or at-home should be repeated after a 15-30 minute rest if they meet the following criteria:

- Hypertension: systolic blood pressure of ≥180 mmHg, diastolic blood pressure ≥105 mmHg, or heart rate of ≥120 bpm
- Hypotension: systolic blood pressure of ≤90 or a diastolic blood pressure of ≤60, and a heart rate <50 bpm

If the subject has a confirmed systolic blood pressure of ≥ 180 mmHg, diastolic blood pressure ≥ 105 mmHg, or heart rate of ≥ 120 bpm, and is symptomatic, the subject should be seen (preferably by the Investigator).

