12.2.3. Recording Adverse Events

All AEs and details for the events will be recorded in the subject's source document and eCRF. An AE should be documented in terms of a medical diagnosis and reported in standard medical terminology when possible. When this is not possible, the AE should be documented in terms of signs and/or symptoms observed or reported. It is important for the Investigator to only record 1 AE per line on the eCRF. Combination events (eg, nausea/vomiting), should be entered as 2 events.

The Investigator must determine the intensity of the AE as defined by:

- Mild: no medical interventions required, short lasting discomfort, and does not interfere with subject's daily activities
- Moderate: activity may be limited, and subject may require minimal medical therapy, intervention, or assistance
- Severe: definitely limits subject's daily activity that may require hospitalization and or intervention/therapy assess whether or not the study drug caused the AE

The Investigator will record whether the AE or AEs led to discontinuation of the subject from the study, record the outcome of the AE (unresolved, resolved, resolved with sequelae, death, or unknown), and determine if the AE is serious.

For this study, AEs and SAEs will be collected beginning with the start of dosing on Day 1 and will end 30 days after the last dose of study drug.

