13.4.2.1.3. Electrocardiogram

The interpretation of electrocardiogram and interval duration measurements by the designated electrocardiogram laboratory cardiologists will be reviewed by the Investigator. Clinically significant deteriorations from Baseline will be reported and summarized as TEAEs.

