13.4.2.1.4. Vital Signs

Change from Baseline to each scheduled measurement will be summarized descriptively. Criteria to identify potentially clinically significant values will be defined in the Statistical Analysis plan.

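### No stated output counts, by arm, the subjects whose hypertension began after the study-drug taper started, although rebound hypertension is a named signal

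*Combined protocol and SAP*

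**What the plan says.** The rationale in Section 3.1 states: "A clinical trial is necessary to assess for a signal of serious hypotension, bradycardia, syncope, hepatotoxicity, or rebound hypertension". Section 6.1 makes safety and tolerability the primary objective.

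**Adverse events.** Section 13.4.2.1.1 states: "Summary tables for TEAEs will include number and percent of subjects experiencing TEAEs by system organ class and preferred term". A subject counts once per preferred term and once per system organ class. A TEAE is any event with onset after study drug has been received, or an existing one that worsens. Under Section 12.2.3, AEs are "collected beginning with the start of dosing on Day 1 and will end 30 days after the last dose of study drug". No summary in Section 7.2.1 or 13.4.2 is divided by onset relative to the study-drug taper.

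**Capture of hypertension.** Section 12.1.2 sets numeric limits and says: "Confirmed instances of meeting criteria for hypertension should be captured as AEs regardless of symptomology". Home blood pressure is taken twice daily from the start of the study-drug taper to the EOS Visit (Sections 7.1 and 12.1.2, Tables 4 and 5).

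**Timing.** The Section 3.3 footnotes give, for the standard schedule, "Study drug taper begins on Day 18" and, after a pause of the opioid taper, "Study drug taper begins on Day 24".

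**Vital signs.** Section 13.4.2.1.4 states: "Change from Baseline to each scheduled measurement will be summarized descriptively". It leaves criteria for potentially clinically significant values to the statistical analysis plan, which Section 13.1 says will be final before database lock. That plan's text is not part of the document reviewed.

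**The concern.** Rebound hypertension is a matter of timing: it is hypertension that appears when the drug is reduced or withdrawn. A count that ignores onset time cannot separate it from hypertension at any other point. The protocol collects suitable data, with twice-daily readings over the period of interest and an AE rule that does not depend on symptoms. It then states no table that uses the timing.

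The single row can also mislead in one plausible direction. Lofexidine is an alpha-2 agonist (Section 10.1.1), and the protocol repeatedly guards against hypotension on it. If active-arm subjects have fewer hypertension events while on full dosing, that early deficit could offset a late excess in the all-period row. At stake is the per-arm count of subjects with post-reduction hypertension, which a pilot meant to inform a pivotal study should deliver.

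**Working it through.** **1. The plan's own precision figure.** Section 13.2 gives 0.2 ± 0.24 at 20 per group and 0.20 ± 0.17 at 40 per group, without event rates. Assuming 0.10 vs 0.30 and the Wald half-width without continuity correction, 1.96 × √[(p1(1−p1) + p2(1−p2))/n]:
- n = 20: 1.96 × √(0.30/20) = 0.240
- n = 40: 1.96 × √(0.30/40) = 0.170
- n = 30 (planned): 1.96 × √(0.30/30) = 0.196

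Both stated figures are reproduced. The same formula is used in step 4.

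**2. Stated outputs against the question.** The question is how many subjects per arm had hypertension with onset after taper start.

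| Stated output | Counts subjects? | Separates onset after taper start? |
|---|---|---|
| TEAEs by class and preferred term, also by severity and drug-related (13.4.2.1.1) | Yes | No |
| Serious TEAEs; TEAEs leading to discontinuation (7.2.1) | Yes | No |
| Vital-sign change from Baseline by measurement (13.4.2.1.4) | No | Yes |
| Vital-sign threshold criteria (left to the analysis plan) | Not stated | Not stated |

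No stated output does both.

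**3. What the single row covers.** Nominal last dose is Day 21 (Day 27 after a pause), so AE collection ends about Day 51 (Day 57). Post-dose blood pressure checks marked in the vital-sign rows of Tables 2 to 5:
- Standard, before the taper: Day 1 post-dose and Days 2, 3, 7, 8, 14, 15 = 7
- Pause, before the taper: the same plus Days 20 and 21 = 9
- Taper start to EOS: 10 diary days × 2 = 20, plus Visit 5 and EOS = 22 on either schedule

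| Onset period | Standard | With a pause |
|---|---|---|
| Before study-drug taper | Days 1–17: 7 checks, 7/17 = 0.41 per day | Days 1–23: 9 checks, 9/23 = 0.39 per day |
| Taper start to EOS | Days 18–28: 22 checks, 22/11 = 2.0 per day | Days 24–34: 22 checks, 2.0 per day |
| After EOS to 30 days after last dose | Days 29–51: none in 23 days | Days 35–57: none in 23 days |

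The middle period is checked about 4.9 times as densely as the first ((22/11)/(7/17)), or 5.1 times with a pause. Those ratios hold only up to EOS. From taper start to 30 days after last dose the rate is 22/34 = 0.65 per day, about 1.6 to 1.7 times the earlier rate. This is why the window should close at EOS, with later onset shown separately. A general instruction in Section 12.1.2 to ask for a reading during phone calls could add up to four checks after EOS (three calls and the 30-day call), or 4/23 = 0.17 per day. That would not change the picture.

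**4. Illustration of offsetting.** All counts are assumed, at 30 per arm, active vs placebo, with early and late cases in different subjects. Onset after taper start is held at 4 vs 1 (13.3% vs 3.3%; difference 10.0 points, half-width 13.8).

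| Earlier onset | All-period row | Difference ± half-width (points) |
|---|---|---|
| 0 vs 0 | 4 vs 1 | 10.0 ± 13.8 |
| 2 vs 2 | 6 vs 3 | 10.0 ± 17.9 |
| 1 vs 4 | 5 vs 5 | 0 ± 18.9 |

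The same late difference appears as 10 points in two cases and as 0 in the third.

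**The case against.** The strongest reply is that Section 13 is expressly an overview, and that both extra analyses and vital-sign thresholds are left to an analysis plan we have not seen. That plan may contain by-visit threshold counts. This stands, and it limits the point to what the protocol states. It does not remove it: the plan need only be final before database lock, whereas Sections 9.1.2 and 13.5 unblind statistical programmers and sponsor-designated reviewers after about 30 subjects. A window chosen after that could be informed by the data.

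It is also fair that change from Baseline at each measurement separates taper and post-taper times, so an average rise would be visible. An average does not say how many subjects had hypertension. The Data Monitoring Committee will look at cardiovascular events, but that is monitoring rather than a stated final analysis.

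The masking case needs early and late counts that happen to cancel, and the other two cases in the illustration leave the difference unchanged. Even the windowed 4 vs 1 has an interval that includes zero. All of this stands: the table would describe the signal, not settle it.

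A reader might infer three stronger things that the documents do not support:
- **That hypotension and bradycardia are also undercounted because events split across terms.** Sections 12.1.2 and 12.2.3 steer investigators to diagnosis-level recording, and nothing shows that coding would split. Serious TEAEs and those leading to discontinuation have their own endpoints. The rationale speaks of serious hypotension and does not list orthostasis.
- **That denser checking during the taper biases the comparison.** Both arms follow the same schedule.
- **That the trial would miss rebound hypertension altogether.** The events would be collected and would appear in the TEAE tables, without their timing.

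**Conclusion.** The point holds for rebound hypertension only. The protocol names the signal and collects the readings, but states no by-arm count of subjects whose hypertension began after the study-drug taper started. The single TEAE row mixes three periods: about 0.4 scheduled checks per day, then 2.0, then none marked.

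The size of the consequence is unknown because the documents give no hypertension rates. Nothing is lost if there are no early cases. Under the assumed counts, a 10-point late difference could appear as anything from 0 to 10 points. The direction of possible masking rests on the drug's class, not on data in the protocol.

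This is a modest improvement worth considering for the primary safety objective, not an error in the design, the sample size or the type I error. The unseen analysis plan may already supply it.

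**What to change.** Add to Section 13.4.2.1.1 one descriptive table, by arm, of subjects with at least one hypertension TEAE, in three rows by onset:
1. Before the study-drug taper.
2. From taper start (Day 18, Day 24 after a pause, or the start of the taper at early discontinuation) through EOS.
3. After EOS through 30 days after last dose, labelled as a period for which the schedules mark no blood pressure checks.

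Count each subject once per row. Give the arm difference with a descriptive 95% confidence interval and no test, in keeping with Section 13.4.2. Use actual dates. Section 8.6 calls for the EOS procedures at discontinuation, possibly before the study-drug taper is finished. For early discontinuers the second row could therefore close 7 days after last dose, matching the nominal EOS timing. The term list should also say whether events that meet the Section 12.1.2 hypertension criterion on heart rate alone are included.

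Fix the terms and windows before the interim unblinding, for example when the Data Monitoring Committee charter is signed.

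The cost is one short term list and one table from data already collected, with no effect on sample size or alpha. One limitation remains: Section 9.2.3 lets the investigator lower the dose from Day 3 (or back to 1 tablet on Day 2), and hypertension after such a reduction falls in the first row. Grouped rows for hypotension and bradycardia are optional.
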